2.0 Background

Molluscum contagiousum (MC) and warts are common viral disease in children. They result from an infection with a double stranded DNA virus (1). Diagnosis is clinical, presenting as smooth, round papules with central umbilication in MC and irregularly surfaced domed lesions in warts. Although benign and generally self-limited, these conditions are contagious and can lead to complications such as inflammation, pruritus, dermatitis, scars and superinfections (2). There is little consensus concerning the management of these conditions. Treatment options include mechanical destruction with cryosurgery or heat, topical irritants, topical vesicants and topical acids (3). These strategies are often irritating and/or painful making application to children very difficult, particularly in cases where many have to be treated at once.

Physical plasma has been considered the fourth state of matter. Biomedical application at lowertemperature plasma have been regarded as one of the most significant opportunities in plasma science. Nonthermal, cold and non-equilibrium plasma synonymously mean plasma that is not in thermodynamic equilibrium because the electron temperature is significantly warmer than heavy species. When the electrons are thermalized their velocity distribution is very different from the ion velocity distribution leading to modification in DNA, proteins and cell membranes. Most NTAP plasmas are generated in helium or argon mixed with a number of reactive gases (7). This creates a low ion energy environment with a rapid reaction response in which UV light and reactive oxygen and nitrogen species induce a focused, transient antiviral or antibacterial milieu (18). NTAP offers direct delivery to the sample surface without the complications of a vacuum chamber to physically burn the tissue and trigger a complex sequence of biological responses in tissue and cells (4). Plasma does not cause lasting damage to the skin or skin functions, indicating a very favorable safety profile for its application in treating cutaneous pathologies (20).

Plasma affects cells in a dosage-dependent manner by disrupting cell-cell adhesion and cell detachment from substrates (12). The short-term exposure temporary causes cell membrane permeabilization, inhibiting cell migration. Longer exposure times and higher intensity plasma induces apoptosis or necrosis by reactive oxygen and nitrogen species. Several pilot studies have confirmed that NTAP induces multiple modes of cell death in human melanoma and hepatocellular carcinoma. The plasma damaged cells begin to repair the damage with releasing growth factors (ex: fibroblast growth factor 2) (12).

Page 2 of 13

In the biomedical field, NTAP has a broad range of applications including disinfection of living tissues, blood coagulation, induction of apoptosis in malignant tissues, a localized modulation of cell adhesion and proliferation and tissue modification of interest in electrosurgery (5-7,9,10). The first small scale clinical studies have shown plasma treatments were well tolerated, painless and, most importantly, without side effects (20-26). In a risk assessment of UV radiation and temperature, it was shown that UV radiation of the plasma is an order of magnitude lower than the minimal erythema dose necessary to produce sunburn on the skin *in vivo*. Additionally, thermal damage of the tissue by the plasma can be excluded since the electrons and ions are not in thermal equilibrium, thereby resulting in "cold," rather than "hot" plasma, which is actually room temperature upon tactile examination. 27).

Multiple modes of NTAP, also known as cold atmospheric plasma (CAP), have been employed in dermatologic clinical studies such as wound healing, onychomycosis, actinic keratosis and viral warts (28). Friedman's case series on warts proved it safety and efficacy in children, reporting no adverse events (blistering, scarring, significant pigmentary alteration or persistent nail changes) or pain reported in treatment (29). A proof-of-concept study on warts in children demonstrated efficacy and exceptional tolerability when treated with plasma as a result of its intracellular calcium influx and viral replication inhibiting effects. In actinic keratosis they had a 70% improvement rate with no discomfort during or after treatment. Onychomycosis had a 50% clinical and 15% mycological cure rate in 13 patients without any side effects. And wound healing of chronic ulcers had decreased bacterial as expected from well-documented inhibitory effects on bacteria and also superior wound healing rates compared to wound care alone. Moreover, it has been shown to be safe and successful in proof-of concept studies exploring its application in the treatment of Verruca vulgaris. Its efficacy in molluscum has not yet been tested.

Given NTAP's outstanding safety profile and painless application (5), its prior proof of concept success in treating common verrucae, and the similarity between verrucae and molluscum, we propose to use NTAP to treat these conditions and expand upon the existing research literature.

If the NTAP device is shown to be a successful, efficacious and painless treatment option for children and adolescents with verrucae and molluscum, this would be a revolutionary and environmentally friendly approach to two of the most common viral infections and chief complaints found during dermatology visits in this age group. The non-toxic, chemical free, waste free, multi-year device results in a significant reduction of effluents, which is beneficial from an economic but also an environmental viewpoint (30).

3.0 Intervention to be studied (if applicable)

We will utilize a floating electrode-dielectric barrier device (FE-DBD) Cold atmospheric plasma (CAP) device on molluscum and warts in children and adolescents 4-21 years (Figure 1). Children and adolescents are targeted because they are the population most affected by painful standard of care therapy. The study will continue until at least 68 warts and 68 molluscum are treated. Each patient will not have more lesions treated than SOC recommendations. Half the lesions will be treated with plasma and the other half with standard of care being cryotherapy for warts and cantharidin for molluscum. A single patient must have minimum of 1 clinically diagnosed lesion treated and maximum of 20 treated. Lesions with a clinical impression of warts or molluscum will be selected. Selection of treatment type (control vs NTAP) will be randomly selected. Lesions

Page 3 of 13

The treatment device in this study generates cold atmospheric plasma. Cold atmospheric plasma has certain properties of plasma, such as ionized gas molecules. To create plasma, a pulse generator supplying 20-kV pulse of 20-ns pulse width at 200 Hz (FPG10-01NM10, FID GmbH, Burbach, Germany) to a 5-mm diameter quartz-covered copper electrode of 10-cm length and 1-mm quartz thickness (5). These nanosecond pulse parameters were chosen to provide sufficient treatment dose at the high level of plasma uniformity required to avoid any tissue damage. We treated the lesions for approximately 1 to 2 minutes each, moving the electrode gently over the treatment area.

After the study treatments are completed, we will analyze the data to see if the treatment was safe and effective.

Non-significant risk device statement (6-19) (Figure 1)

- We are proposing a clinical trial floating electrode-dielectric barrier device (FE-DBD) a Cold Atmospheric Plasma (CAP) device.
- While novel to the medical field and especially to dermatology, there are already a number of publications regarding its use on human skin in adults (20-26) and children (29).
- CAP devices utilize noble gases (such as helium) to deliver plasma state matter to the skin. As
 its name implies, the generated plasma stream is of near skin temperature and it exists on
 normal atmospheric pressure. During the generation of the plasma there is no electric contact
 with the patient. The treatment does not increase skin surface temperature and the used helium
 gas the same as used for balloons being a noble gas does not develop a chemical reaction
 with the skin. The flow of the gas is slow, thus there is no mechanical effect on the skin.
- Previous clinical studies used these devices on skin surfaces that were denude, eroded or ulcerated and even without intact skin barrier function there were no reported adverse effects. In fact, one study specifically examined the tolerability of plasma treatments of various equipment and found that the plasma was well tolerated and had no adverse effects on the skin surface.
- Based on the principles of the treatment as well as the below referenced prior studies we believe that this non-invasive method of treatment will be performed using equipment that certainly qualifies for a minimal-risk device that will not harm normal skin.

[figure not shown]

Fig. 1. Floating-electrode DBD plasma. Top panel: pulse generator and hand-held electrode. Bottom panel: Plasma is being generated using the electrode tip. The electrode connected to the pulse generator must be kept near the treated surface. Either the tip or the side of the electrode can be used, but plasma will only form where the gap between the electrode and the target surface does not exceed 1 mm. This device pictured will be used in our trial.

Clinical safety of plasma (28):

Standards are issued by the national regulatory authorities like UV radiation, ozone, nitrogen oxide and electrical current. Assuring compliance to maintained through measuring values for every CAP device and exposure limits. The presence of reactive species raises a concern for the mutagenicity of CAP; however, all devices were found safe within the operating parameters studied. To ensure safety of each CAP device, everyone must be tested on standards developed by the International Organization on Plasma Medical Device and Standardization (IOPMS) with [name] representing the US. IOPMS is considering device safety under the major aspects:

Page 5 of 13

- biomedical safety, related to optimization of protocols, suppression of side effects, detailed analysis of clinical studies.
- (ii) physical, technological, and electric safety, related to limitations of generation of ozone, UV radiation, leak currents, electromagnetic interaction with other devices in medical environment
- safety aspects related to device (and treatment protocol), sensitivity to device positioning, dosimetry, environmental conditions

Dermalite dermatoscopes will be used to assess diagnosis and resolution. They are approved by the FDA for the study indication. Dermoscopy, also known as dermatoscopy, epiluminescence microscopy, incident light microscopy, or skin surface microscopy, is performed using a handheld instrument called a dermatoscope or dermoscope, which has a transilluminating light source and standard magnifying optics (10x). The dermatoscope facilitates visualization of subsurface skin structures located within the epidermis, dermoepidermal junction, and papillary dermis, which are otherwise invisible to the unaided eye. Colors and structures visible with dermoscopy are required for generating a correct diagnosis.

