6.0 Number of Subjects

Total of 150 would be required (half control, half NTP) to achieve 80% power with an alpha of

.05.

Calculation:

- Assumption for Probabilities for the Null hypotheses is P1=P2=P3=1, hence P1 = .333333, P2 = .333333, P3 = .333333 and P1+P2+P3 = 1.0 or that each proportion has an equal chance.
- Assumption for Probabilities for Alternative Hypothesis is taken from Provided NTP paper where P1=9/17 (Full Resolution = .53), P2=3/17=.18 (Some Improvement), and P3=5/17=.29 (no improvement).

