10.0 Study Design / Methods

- A chart review of patient the patient's medical record will be completed and the following information will be collected for research purposes: DOB, demographics, contact information and diagnosis.
- Skin irritants, emollients, topical medications and other topical products cannot be applied to the study area 4 weeks prior to the start of the study and throughout the duration of the study. Details of what can and cannot be used can be discussed any time.
- During a clinical care visit, if a patient is eligible and agrees to participate, lesions will be selected by the dermatologist prior to procedure. The lesions will be marked randomly for a certain treatment regimen and photographs will be taken before each treatment and after completion of the study. Identifiers will be covered to protect identity. All images will be saved on a MUSC network secure box drive using a subject study number.
- The number of lesions treated will not exceed SOC recommendations. They will be determined by provider assessment and anatomical location.
- Participants with one lesion will receive either NTAP or standard of care (SOC). SOC is

Page 8 of 13

cryotherapy for warts and cantharidin for molluscum. Participants with greater than 2 lesions will receive equal treatment of NTAP and SOC. The number of lesions treated will be based off the providers assessment and anatomical location. Treatment of a single lesion or an odd number of multiple lesions will be based off a randomized list.

- All SOC lesions will be treated first to reduce the number of patients not wanting return to the more painful modality.
- All people in the room will be provided eye shields that must be worn during treatment. The patient will be placed in a comfortable position before the lesion is cleaned with alcohol.
- Each lesion will be treated for 1-2 minutes. Total treatment duration will be no longer than 20 minutes.
- The interval between treatment groups will about 1 minute.
- There will be a follow-up phone call a week after treatment to check on resolution and report any adverse events. If an adverse event is reported the study team members will access if the patient needs to be seen by a provider that day.

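### The plan ties 80% power to a total of 150 with no stated unit, but its only study-level completion rule allows a stop at 136 lesions, and the visible text does not link the two

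*Combined protocol and SAP*

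**What the plan says.** Section 6.0 of the protocol gives the sample size: "Total of 150 would be required (half control, half NTP) to achieve 80% power with an alpha of" .05. The heading is "6.0 Number of Subjects", but the sentence itself names no unit and does not say whether warts and molluscum are pooled. The inputs shown are a null of "P1 = .333333, P2 = .333333, P3 = .333333" and an alternative of "P1=9/17 (Full Resolution = .53), P2=3/17=.18 (Some Improvement), and P3=5/17=.29 (no improvement".

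Section 3.0 says when the study is complete, and it counts lesions: "The study will continue until at least 68 warts and 68 molluscum are treated". It also sets the split, "Half the lesions will be treated with plasma and the other half with standard of care", and the range per child: "A single patient must have minimum of 1 clinically diagnosed lesion treated and maximum of 20 treated". Lesion numbers are further limited by standard-of-care recommendations.

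Section 10.0 assigns a child with one lesion to one treatment and adds: "Participants with greater than 2 lesions will receive equal treatment of NTAP and SOC". Its sentence about study cessation at the 4-week visit concerns the individual child and is not a rule for the study. Section 14.0 permits withdrawal but gives no rate.

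**The concern.** A sample size section and a completion rule should describe the same study. Here one gives a total of 150 under a heading about subjects, and the other gives two lesion counts that sum to 136. No visible sentence converts lesions to children, adds an allowance for loss, or makes 150 a condition for closing enrolment.

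The 80% power claim is thus attached to a size that the completion rule does not require. A reader cannot tell when enrolment is complete, in which unit, or what power the study has at that point. In principle, two people could read the same protocol and disagree on whether enough children have been enrolled.

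**Working it through.** **Inputs.** Total 150, alpha .05, power 80%, and the null and alternative proportions (Section 6.0). Floors of 68 and 68, half split, 1 to 20 lesions per child (Section 3.0). Chi-square analysis (Section 11). The plan gives 1/3 only as a null value; using it as the control response is an assumption. All power figures treat lesions as independent.

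**1. The plan's own figure.** The calculation behind 150 is not shown. Results at 80% power and alpha .05:
- One-sample goodness of fit, (9, 3, 5)/17 against equal thirds: 50.
- Two-arm 2x3 chi-square, control at equal thirds: 203 in total.
- Two proportions, 9/17 vs 1/3, pooled variance: 99 per arm two-sided, 78 per arm one-sided.
- One-sided, rounded to .53 vs .33: 74.7, so 75 per arm, or 150.

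Only the last matches, and it needs a one-sided test and a rounded control value that the plan does not state. Whether 150 can be reproduced is a separate issue; this route serves below as one illustration.

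**2. If 150 counts lesions.** Minimum at completion: 68 + 68 = 136. Largest shortfall: 150 − 136 = 14, and 14/150 = 9.3%.

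The floors are joint and neither condition is capped, so a stop at exactly 136 requires that neither condition has passed 68 when the other reaches it. As an illustration, assume equal accrual, one lesion per child and one condition per child. The chance of exactly 136 is C(136,68)/2^136 = 0.068, and the expected total is 136 + 136 × 0.068 = 145. With 55:45 accrual, the mean total is about 152. The documents give no accrual figures, so these only show that 14 is a maximum.

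**3. Power at 75 and 68 per arm.** For two proportions, power = Φ{[δ√n − z√(2p̄q̄)] / √(p1q1 + p0q0)}. With .53 vs .33, δ = .20, 2p̄q̄ = .4902, p1q1 + p0q0 = .4702 and one-sided z = 1.645:
- n = 75: (1.732 − 1.152)/.686 = 0.846, power 80.1%.
- n = 68: (1.649 − 1.152)/.686 = 0.726, power 76.6%.

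| Test | 150 total | 136 total | Loss (points) |
|---|---|---|---|
| One-sided, .53 vs .33 | 80.1% | 76.6% | 3.5 |
| Two-sided, .53 vs .33 | 70.0% | 65.7% | 4.3 |
| 2x3 chi-square (w² = 0.0476, df 2) | 66.5% | 61.9% | 4.6 |

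**4. If 150 counts children.** Each child has at least 1 treated lesion, so a stop at exactly 136 lesions gives at most 136 children. At 20 lesions each, 68/20 = 3.4, so 4 children per condition, or 8 in all if no child has both conditions, would meet the floors. Eight is an arithmetic extreme, not a forecast. A larger lesion total could come from more children, but the rule does not ensure 150 under any of these patterns.

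**5. Precision at the minimum.** 95% half-width = 1.96 √[(p1q1 + p0q0)/n], with p1 = 9/17 and p0 assumed from 1/3 to .53:
- n = 68 per arm, pooled: 16.3 to 16.8 points.
- n = 34 per arm, one condition, if the half split holds there: 23.1 to 23.7 points.

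These are best cases before clustering, and the pooled figure combines two comparators, cryotherapy and cantharidin.

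**The case against.** The strongest reply is that the two statements can both be met. The Section 3 rule is a minimum, and 75 warts plus 75 molluscum would satisfy both sections. Because the floors are joint, the rule itself will often carry the total above 136, sometimes past 150. This stands. It makes 14 lesions and the 3.5 to 5 points upper bounds, and it rules out calling the passages a direct contradiction. It does not make 150 a requirement.

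A second reply is that the equal split in Section 6 echoes the lesion split in Section 3, so 150 probably means lesions. That is a fair inference. The phrase fits children poorly, since those with more than two lesions receive both treatments (the case of exactly two is not clearly covered). But the section heading points the other way, and the plan does not settle it.

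A third is that 150 may be 136 with about 10% added: 136 × 1.10 = 149.6. No attrition rate is given, and dividing by 0.90 would give 152 (76 per arm). This is conjecture.

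Finally, a linking sentence may be missing from the text as supplied. The lesion paragraph in Section 3.0 breaks off mid-sentence, and the section numbers run from 11 to 14. The point is therefore limited to the visible text.

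**Conclusion.** The concern holds as an unreconciled pair of targets. Section 6 attaches 80% power to 150 of an unnamed unit, and the Section 3 rule secures only 136 lesions.

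On the lesion reading, the gap is between 0 and 14 lesions (at most 9.3%), and the power cost is at most about 3.5 to 5 points. That rests on an assumed control response of about one third and on independent lesions. On the subject reading, 150 is not secured at all, and the size of the gap depends on lesions per child, which the plan does not give.

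A reader might infer that the study will finish 14 short, or that this mismatch alone leaves it badly underpowered. The documents support neither: 136 is a floor, and the loss from 150 to 136 is small. The lower power levels in the two-sided and 2x3 rows come from how 150 was derived, which is the separate issue. This should be fixed, but it is a matter of wording and disclosure.

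**What to change.** State one unit and one number in Sections 3 and 6, and report the number of children alongside lesions.

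**Without added enrolment.** Restate Section 6 as the Section 3 minimum: 136 lesions, 68 per arm pooled, and 34 per arm in each condition if the half split holds there. Replace the 80% figure with the power that this minimum delivers for the planned two-arm comparison. Give the test and its sidedness, and state the control response and within-child clustering as assumptions, since the documents supply neither. Label any half-width (about 16 to 17 points pooled, 23 to 24 per condition) as a best case before clustering. The cost is wording, one short recalculation and a less favourable stated power. This discloses the power and does not raise it.

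**Keeping 150 as lesions.** Say so in Section 6, and write in Section 3 that treatment of new lesions continues until there are at least 68 of each condition and at least 150 in total. This adds at most 14 lesions to the minimum. The calculation behind 150 should still be shown.

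**If 150 is meant as children,** the Section 3 rule must count children too. The added enrolment cannot be sized without a figure for lesions per child.

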1.0 Objectives / Specific Aims

- Objective: Study the safety and efficacy of uniform nonequilibrium, nonthermal atmospheric pressure plasma (NTAP)/cold atmospheric plasma device (CAP) in the treatment of molluscum contagiosum and vercurra (warts) in children 4-21 years.
- Aim:
 - Measure the changes in size, pain and appearance of verrucae and molluscum after 4, 8 and 12 weeks.
 - Evaluate the safety profile and patient tolerability of the treatment by analyzing potential side effects and pain levels, or lack thereof, with each treatment.
- Hypothesis: NTAP will be an equally efficient and painless alternative to cryotherapy for the treatment of molluscum and warts.

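### Similarity to an active comparator in self-limited disease cannot show that NTAP is effective; the efficacy conclusion should be limited to NTAP relative to the named standard of care

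*Combined protocol and SAP*

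**What the plan says.** Section 1.0 (Objectives / Specific Aims) sets out to study the safety and efficacy of NTAP. Its hypothesis is relative: "NTAP will be an equally efficient and painless alternative to cryotherapy for the treatment of molluscum and warts". Section 3.0 states the purpose of the analysis in absolute terms: "After the study treatments are completed, we will analyze the data to see if the treatment was safe and effective".

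The comparator is given in section 3.0: "Half the lesions will be treated with plasma and the other half with standard of care being cryotherapy for warts and cantharidin for molluscum". Section 10.0 repeats it. No lesion is assigned to sham or to no treatment.

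On natural course, section 2.0 says: "Although benign and generally self-limited, these conditions are contagious and can lead to complications". It gives no rate of spontaneous clearance. It also cites no result for cryotherapy or cantharidin against no treatment, and says only that opinion on management is divided. The Study Endpoints section grades response as none, partial or complete at 4, 8 or 12 weeks. Section 5.0 excludes lesions that already show signs of resolving on their own. Section 2.0 says NTAP has not yet been tested for efficacy in molluscum.

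The analysis is one line under Data Management: a chi-square comparison of success proportions, with a parenthesis about equal-chance outcomes. No margin and no criterion for calling the treatment effective is given.

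**The concern.** Lesions in either arm may clear during up to 12 weeks of follow-up with no help from treatment. The result the trial hopes for, NTAP doing as well as SOC, is what two effective treatments would produce. It is also what two inactive treatments would produce if both simply followed the natural course. Without an untreated reference, or a benchmark for natural clearance or for SOC, nothing in the data separates these two cases.

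At stake is the wording of the conclusion. Spontaneous clearance could be credited to a new device used in children. This matters most for molluscum, where the protocol has no earlier efficacy evidence to lean on.

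The point is separate from the absence of an equivalence margin. A margin addresses whether the arms are close. It does not address whether closeness means benefit, since two inactive treatments really are equivalent.

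**Working it through.** **The plan's own figure.** Section 6.0 states: "Total of 150 would be required (half control, half NTP) to achieve 80% power with an alpha of" .05. The null is one third in each response category; the alternative is 9/17, 3/17 and 5/17.
- One-sample goodness of fit: w² = 3 × [(0.529 − 0.333)² + (0.176 − 0.333)² + (0.294 − 0.333)²] = 0.194. For 80% power on 2 df the noncentrality is 9.63, so N = 9.63 / 0.194 ≈ 50.
- Two-arm 2×3 chi-square: about 102 per arm. With 75 per arm the power is 66.5%.

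I could not reproduce 150 with a standard two-arm calculation (3 × 50 gives it only arithmetically). For the present point, what matters is that neither a natural-clearance rate nor an SOC rate enters the sizing.

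**Inputs for the check.**
- From section 3.0: at least 68 lesions per disease, half per arm, so n = 34 per arm per disease. Analysis by disease is my assumption. The unit of the 150 in section 6.0 is not stated, and 68 + 68 = 136 does not match it, so 68 and 75 per arm were also tried.
- From section 6.0: alpha .05, taken as two-sided.
- Assumed: natural 12-week clearance r from 5% to 40%, because the documents give none; independent lesions.

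**Step 1: both treatments inactive, between-arm test.** Both arms clear at r, so the null is true and P(not significant) ≈ 1 − alpha = 95% whatever r is. Simulation (40,000 trials per setting) gives the second column of the table. The 2×3 version, and 68 or 75 per arm, also stay within 94% to 97%. If several lesions per child are split between arms (assumed intraclass correlation 0.2 to 0.5), the figure is about 97% to 99%.

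**Step 2: both inactive, with a margin.** Take an illustrative 20-point margin and require the lower 95% limit for NTAP minus SOC to exceed −0.20. Approximately, P(pass) = Φ(0.20/SE − 1.96), with SE = √[2r(1 − r)/n]. At r = 20% and n = 34: SE = √(0.32/34) = 0.097, and Φ(2.06 − 1.96) = Φ(0.10) ≈ 54%; simulation gives 55%. The fall down the third column reflects sample size and margin, not protection from natural clearance. With 75 per arm the pass rate rises to between 72% and nearly 100%.

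**Step 3: NTAP inactive, SOC active.** Let NTAP clear at r and SOC at 53%. That rate is borrowed from the NTAP alternative in section 6.0, as the documents give no SOC rate. The fourth column shows how often the test would miss the difference.

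| r | Both inactive: not significant | Both inactive: passes 20-point margin | NTAP inactive, SOC 53%: not significant |
|---|---|---|---|
| 5% | 96.6% | 95% | 0.1% |
| 10% | 94.4% | 80% | 1.5% |
| 20% | 94.8% | 55% | 16% |
| 30% | 94.6% | 45% | 50% |
| 40% | 94.7% | 40% | 82% |

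All at n = 34 per arm; margin figures are good to about one point.

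**Step 4: chi-square against equal thirds.** If the planned test is instead goodness of fit of the NTAP arm against thirds, the 95% does not apply. Take purely spontaneous mixes (complete/partial/none) at n = 34. The test rejects in about 99% of trials at 20/10/70, 48% at 30/20/50 and 29% at 40/20/40. For the first, the noncentrality is 34 × 3 × (0.133² + 0.233² + 0.367²) ≈ 21, against a critical value of 5.99. Rejection measures distance from thirds in any direction, so this reading offers no natural-clearance benchmark either.

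**The case against.** Several things count on the other side.

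- *The hypothesis is relative, and the relative comparison is protected.* Allocation is random and the grading is blinded, so natural clearance is expected to balance between arms. This stands. The weakness lies only in the step from similarity to effectiveness.
- *An active comparator is a legitimate choice.* Section 2.0 describes contagion and complications. This stands too, and nothing here asks for an untreated arm.
- *Lesions already resolving are excluded.* That reduces the problem but does not remove it, because resolution can begin after entry.

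Three stronger readings are tempting, and the documents do not support them.

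- A reader might infer that the trial is committed to declaring NTAP effective whenever it does not differ from SOC, and so will be wrong 95% of the time when neither works. Section 3.0 says only that the data will be examined for safety and effectiveness. No rule turns non-significance into effectiveness. The 95% is 1 − alpha under an assumed rule and would appear in any two-arm trial with equal true rates.
- A reader might infer that the conclusion does not depend on whether NTAP has any effect. Step 3 shows otherwise: with SOC at an assumed 53% and natural clearance of 5% to 20%, an inactive NTAP would escape detection in only 0.1% to 16% of trials.
- A reader might take the divided opinion on management as a statement that SOC does not work. Section 2.0 does not say that.

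**Conclusion.** The concern holds in a limited form. The protocol has an efficacy objective and asks whether NTAP was effective. Yet the lesions are self-limited and the only comparator is active, with no untreated reference, natural-clearance rate or evidence of SOC against no treatment. Similarity to SOC therefore cannot separate both working from neither working. A margin alone would not cure this.

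Its size is conditional. If non-significance were read as equal efficacy and hence as effective, two inactive treatments would reach that conclusion in about 95% of trials. This assumes independent lesions and a two-sided between-arm test at .05; the reading rule is not in the documents. Under a test against equal thirds the figure does not apply, but thirds are not a natural-clearance benchmark. The problem concerns absolute efficacy only. A clear advantage of NTAP over SOC would be a different matter, provided SOC is no worse than leaving lesions alone, but that is not the stated hypothesis.

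**What to change.** In sections 1.0 (Objectives / Specific Aims) and 3.0:

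1. Limit the efficacy conclusion to NTAP relative to the named SOC within each disease, as section 3.0 names it: cryotherapy for warts, cantharidin for molluscum. The hypothesis in section 1.0 names only cryotherapy for both diseases and must be reconciled with sections 3.0 and 10.0.
2. State that similarity to SOC will not be reported as evidence that NTAP is effective, because the lesions are self-limited and there is no untreated reference.

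The cost is wording in two sections and a more modest efficacy claim. No visit, treatment or sample size changes.

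I would not try to build a natural-course reference from lesions left over under the treatment cap ("The number of lesions treated will not exceed SOC recommendations"). Nothing in the protocol says that eligible lesions will be left over, or will stay untreated and followed. The dermatologist chooses which lesions are treated, so any remainder would be a selected group. Participation may also end once the treated lesions clear.
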